Following the group sessions, participants will receive individual, collaborative goal-setting sessions with an individual session provider, another VA staff member who is a regular provider of diabetes care in VISN12, who is trained by the study staff to lead these goal-setting sessions. Individual sessions will follow the group sessions at a mutually convenient time. The individual session provider will be trained to a) conduct collaborative goal-setting for diabetes self-management and b) understand how to use measures of patient activation and FHL personalized to each patient-participant to enhance the collaborative goal-setting process. Designated VISN12 staffers undergoing EPIC training will be consented as research subjects and must complete an intervention fidelity assessment prior to qualification for the active intervention (§ 5.1.F.).

Patients enrolled in the EUC arm will receive routine PACT visits and “enhanced usual care” (EUC). Patients randomized to EUC will be referred to the PACT RN Care Manager for diabetes management, and will also receive a packet of educational materials regarding diabetes management, including a letter delineating the diabetes management resources available at their facility. The PACT RN will be directed to provide care as usual. Patients

enrolled in EUC will not receive group or individual goal-setting information defined by the EPIC protocol and their PACT teamlets will not receive personalized information about patient activation or FHL.

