Table 8: Patient Activation and Health Literacy Goal Setting Tool

		Activation – Having the knowledge, skill, and confidence for chronic disease self-	
		Low Activation	High Activation
Health Literacy - The ability to perform basic reading and numerical tasks required to function in a health environment			
	Low Literacy	
Description of Veteran:
 
 
• Believes someone else will manage diabetes
 
• Has limited knowledge and skills regarding self-care and diabetes management
 
• Lacks confidence in ability to manage diabetes
 
• Focused on the present more than long term consequences
 
• May have difficulty understanding complex health messages
 
• May suffer from depression
 
 
Provider Actions to Take:
 
 
• Ask about what motivates Veteran
 
• Set smaller, specific goals, walk through steps to achieve goals and reinforce each achievement
 
	
Description of Veteran:
 
 
• Ready to work on making changes, but unsure about what changes to make
 
• May have difficulty understanding complex messages
 
 
Provider Actions to Take:
 
 
• Ask about what is currently motivating Veteran and reinforce positive actions
 
• Help Veteran identify and overcome challenges that are preventing self-management
 
• Evaluate knowledge gaps by asking about his or her understanding of diet and medication
 
• Present essential information first in a simple format
 
• Ensure understanding by asking Veteran to repeat back information
 

		
 
• Ensure understanding by asking Veteran to repeat back information
 
• Present essential information first if in written format
 
• Consider referral for depression screening
 
	
 
• Help patient create tools with visual diabetes management (ex: medication specific times and pictures instead of twice daily)
 

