**5.1.1.d. Predictors and Mediators of Intervention Outcomes.** **1. Self-Efficacy for Diabetes Self-Management** is an eight-item instrument (Cronbach's  $\alpha = 0.83$ ) that measures confidence in performing specific diabetes management tasks with a per item mean of  $6.87 \pm 1.8$ . It has demonstrated correlation with HbA1c levels. **2. Medication Adherence.** We will measure adherence to prescribed diabetes medications using pharmacy refill records from the Corporate Data Warehouse. For each identified medication we will calculate medication possession ratios and refill gaps (See Attachment 7, 8, and 11). We will also capture by self-report the Morisky Medication Adherence scale. This scale allows for identification of patients at highest risk for poor outcomes due to non-adherence as well as recognition of barriers to medication compliance. Responses are scored using a dichotomous scale (yes = 0; no = 1) with higher scores reflecting better medication adherence. The scale has been shown to have good concurrent and predictive validity as well as high internal consistency, indicating good reliability (Cronbach's  $\alpha = 0.83$ ). **3. Depression Symptoms.** The PHQ-8 is an eight-item instrument (Cronbach's  $\alpha = 0.83$ ) that measures depressive symptoms. **4. Exercise.** The Lorig Exercise scale is a six item instrument that measures exercise behavior during a typical week. No Internal reliability reported; test re-test for stretching and strengthening  $r = .56$ ; test-retest for aerobic exercise  $r = .72$ . **5. Diet.** The Diet scale is a ten-item (Cronbach's  $\alpha = 0.73$ ) instrument developed as part of the Diabetes Self-Care Activities survey, a 25- item instrument that measures perceived adherence to diabetes self-care recommendations. **6. Goal-Setting Evaluation Tool for diabetes (GET-D)** is an objective rater scale developed and validated for scoring the quality of goals and action plans articulated by patients in our prior goal-setting

studies (see Attachment 7, 8, and 11). 5. Treatment Fidelity. We will also use a measure, described in § 5.1.F.iii., to objectively rate staff member fidelity to the intervention.

Table 10. Measures	Screen	Baseline	4 M	10 M	Measure	Baseline	4 M	10 M
Screening protocol	X				Intervention Mediators and Moderators			
Primary outcome variables					PHQ-8 Diabetes Self-Care Self-Efficacy	X	X	X

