Several variables will be examined as separate mediators of the relationship between intervention group (EPIC versus EUC) and post-intervention outcome variables: 1) patients' perceptions of goal-setting engagement by the designated PACT member (CSQ), 2) objective ratings of goal and action plan quality (GET-D), 3) self-efficacy for diabetes self-management, 4) diabetes self-management adherence, and 5) mediation adherence. For each mediator, we will conduct three separate models to test for mediation between intervention group and each outcome: 1) the first model will regress post-intervention HbA1c levels on treatment group and baseline HbA1c levels, 2) the second model will regress the mediator on treatment group and baseline HbA1c levels, 3) the third model will regress post-intervention HbA1c levels on treatment group, baseline HbA1c levels, and the mediator. Parallel analyses will be conducted to predict change in DDS. We will use bootstrapping methods to calculate the unstandardized estimate of the indirect effects as well as unbiased confidence intervals. Significance will be established if the 95% confidence interval of the indirect effect does not include zero. Bootstrapped analyses will be performed using MPlus Version 6.

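### PHQ-8 is collected at all three assessments as a candidate mediator or moderator but has no stated analysis, so depression is left as an unadjusted confounder in the exploratory mediation models

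*Combined protocol and SAP*

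**What the plan says.** - **Where PHQ-8 is listed.** Section 5.1.I has a paragraph headed "Predictors and Mediators of Intervention Outcomes". Its third item is depression symptoms: "The PHQ-8 is an eight-item instrument". Table 10 puts PHQ-8 under "Intervention Mediators and Moderators", collected at baseline, 4 and 10 months.
- **What the mediation analysis uses.** Section 5.6.C.iii, under exploratory analyses, says: "Several variables will be examined as separate mediators of the relationship between intervention group (EPIC versus EUC) and post-intervention outcome variables". The list opens with perceived goal-setting engagement (CSQ) and continues: "objective ratings of goal and action plan quality (GET-D), 3) self-efficacy for diabetes self-management, 4) diabetes self-management adherence, and 5) mediation adherence". PHQ-8 is not on it.
- **What is in each model.** Each mediator gets its own three regressions, and "the third model will regress post-intervention HbA1c levels on treatment group, baseline HbA1c levels, and the mediator". Parallel models are planned for DDS. Mediation is declared when the 95% interval of the indirect effect excludes zero.
- **Depression in the intervention.** In Table 8 (Section 5.1.F), both low-activation cells include the prompt "Consider referral for depression screening". The high-activation cells do not. For control patients, Section 5.1.A says "their PACT teamlets will not receive personalized information about patient activation or FHL".

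**The concern.** Randomisation protects two of the three relations in a mediation analysis: treatment to mediator and treatment to outcome. It does not protect the third, mediator to outcome, which is an observational association within arms. A variable that is related to the mediator and also affects the outcome biases that association and hence the indirect effect.

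Depression is a plausible variable of this kind. Self-efficacy is self-reported, and DDS measures psychological burden (Section 5.1.I.b). Table 8 itself mentions possible depression in the same cell that describes patients as lacking self-efficacy. The plan collects the measure needed to address this but gives it no role as mediator, moderator or covariate.

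At stake is the explanation of how EPIC works. The background (Section 2.A.iii) cites mediation by self-efficacy in the prior trial, so a similar statement from this trial would carry weight.

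**Working it through.** **Sample size, to fix the scale.** Section 5.6.A starts from 100 per arm for d = 0.40. Design effect = 1 + (12 − 1) × 0.0183 = 1.2013, so 100 × 1.2013 = 120 per arm. 120 / 0.85 = 141.2, rounded up to 142 per arm, 284 in total. The plan's figure reproduces. About 240 patients are left after attrition (2 × 120, or 284 × 0.85 = 241). The plan gives no figure for the mediation analysis.

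**Algebra.** Work in SD units with signs aligned. Suppose the mediator M has no true effect on the outcome. Let a = EPIC's total effect on M, r = within-arm correlation of M with PHQ-8, and b = effect of PHQ-8 on the outcome. Leaving PHQ-8 out gives M a coefficient of r × b, so

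spurious indirect effect = a × r × b.

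EPIC's effect on PHQ-8 does not appear in this formula except through a.

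**Setting A (all inputs assumed).** n = 240, 2,000 runs, a = 0.4, EPIC shifts PHQ-8 by 0.4 SD. Monte Carlo 95% intervals stand in for the bootstrap.

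| r | b | 0.4 × r × b | Interval excludes 0, planned model | Same, with PHQ-8 in the model | Planned model, EPIC has no effect on PHQ-8 |
|---|---|---|---|---|---|
| 0.2 | 0.2 | 0.016 | 8% | 4% | 7% |
| 0.2 | 0.4 | 0.032 | 18% | 4% | 16% |
| 0.4 | 0.2 | 0.032 | 18% | 4% | 18% |
| 0.4 | 0.4 | 0.064 | 52% | 4% | 55% |

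The last column barely differs from the fourth. With r = 0.6 and b = 0.4 the planned model reaches 83%.

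**Setting B (all inputs assumed).** n = 241, outcome DDS with a baseline slope of 0.5. EPIC raises self-efficacy directly by 0.4 SD and lowers PHQ-8 by 0.15 SD. Both links (PHQ-8 to self-efficacy, PHQ-8 to DDS) have size L, so a = 0.4 + 0.15 × L.

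- L = 0.3: (0.4 + 0.045) × 0.3 × 0.3 = 0.040. Simulated 0.041; false mediation 35%, or 4% with PHQ-8 in the outcome model.
- L = 0.4: (0.4 + 0.06) × 0.4 × 0.4 = 0.074. Simulated 0.074; false mediation 77%, or 5% with PHQ-8 in the outcome model.
- A different residual scaling gives 30% and about 70% for these two cases. At L = 0.2 the rate is 8% to 10%; at L = 0.1 it is about 5%, the nominal level.

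**How much comes from the Table 8 prompt.** Set EPIC's effect on PHQ-8 to zero in Setting B. The spurious effect becomes 0.4 × L × L = 0.036 or 0.064, which is 0.036 / 0.040 = 90% or 0.064 / 0.074 = 86% of the figures above. Keep the PHQ-8 effect and drop the direct self-efficacy gain instead: 0.15 × L × L × L = 0.004 or 0.010, with false mediation in 2% to 4% of runs. The bias is almost wholly ordinary mediator-outcome confounding.

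**What each remedy does.**
- A sixth separate mediator model estimates the PHQ-8 path but leaves the self-efficacy estimate as it was.
- Baseline PHQ-8 as a covariate cut the spurious effect by about 35% to 45% in simulation. The gain depends on how closely 4-month PHQ-8 tracks baseline, which the documents do not give.
- A joint model with 4-month PHQ-8 removes the spurious effect if PHQ-8 precedes self-efficacy. If the order is reversed (self-efficacy lowers PHQ-8, which lowers DDS), the planned model recovers the true indirect effect of 0.036 to 0.064 SD and the joint model returns about zero.

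**The case against.** - **The analysis is exploratory.** This stands. No H2 or H3 estimate and no sample size figure depends on it.
- **PHQ-8 has no fixed role.** Both headings pair mediators with something else (predictors, moderators), so the plan never promises PHQ-8 as a mediator. Group attendance sits under the same Table 10 heading and is not a mediator in 5.6.C.iii either. This stands in part: attendance does get an analysis, as a predictor in the Aim 1 regressions, while PHQ-8 gets none.
- **Baseline PHQ-8 could enter through the p < 0.25 rule for baseline differences (Section 5.6.C, Aim 2).** It could, but the three mediation regressions list their terms without it. In any case the rule selects on chance imbalance between arms, not on relation to mediator and outcome.
- **The links are assumed.** This stands. With weak links the false rate is close to nominal.
- **A joint model can err the other way.** This stands. Both variables are measured at 4 months and nothing in the documents orders them, so the joint model cannot be the main analysis.

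A reader might also infer from Table 8 that EPIC steers patients into depression care and that this effect will be credited to self-efficacy or goal quality. The documents do not support that. The prompt is only to consider a screening referral, in low-activation cells. Section 6.0 provides for calls in both arms after a 20% rise in symptoms (of unspecified type). The prompt accounts for little of the bias. Goal quality (GET-D) is an objective rating by staff blinded to assignment (Table 5), so the argument about self-report does not carry over to it.

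**Conclusion.** The gap is real and modest in consequence. PHQ-8 is measured three times as a candidate mediator or moderator, no analysis uses it, and the single-mediator models leave depression free to confound the path from self-reported mediators to the outcome, DDS in particular. This holds whether or not EPIC changes depression.

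The size cannot be fixed from the documents. With links of 0.2 to 0.4, a self-efficacy gain of about 0.4 SD and no true self-efficacy effect, the spurious indirect effect is 0.016 to 0.074 SD, or 4% to 18% of the planned d = 0.40 (0.016 / 0.40 and 0.074 / 0.40). The plan's rule then declares mediation in roughly 8% to 80% of trials. These are illustrations, not predictions. What is at risk is the stated mechanism of EPIC, not whether it works.

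**What to change.** In Section 5.6.C.iii:

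1. Add PHQ-8 as a sixth mediator for both HbA1c and DDS, in line with Section 5.1.I and Table 10.
2. Include baseline PHQ-8 as a covariate in all mediation models. It is measured before randomisation, so it cannot lie on the path from treatment.
3. Report a joint model with 4-month PHQ-8 as a sensitivity analysis. State that the order of PHQ-8 and self-efficacy at 4 months is not identified, and that the joint model understates the self-efficacy path if PHQ-8 lies downstream of it.

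The cost is a few lines of text, one more exploratory indirect effect per outcome and a little more analysis. The data and Mplus are already in the plan. Some confounding by change in depression after baseline will remain in the main mediation models, and the report should say so.

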### **5.1.G. Study Variables**

**5.1.G.a. Fidelity Measures.** We will also measure, as described in **§ 5.1.F.iii.**, fidelity to the intervention in the domains of adherence and proficiency. 1. Objective ratings for individual session providers. For individual session provider, adherence and proficiency will be rated after providers have completed the training, prior to the first personalized goal-setting session, in the form of a role-play assessment. Providers who fall below an acceptable level of adherence and proficiency will receive consultation by the study team to address concerns and will be asked to repeat the role-play exercise until an acceptable level is achieved. 2. Objective ratings for group leaders. For group leaders, we will determine adherence ratings based on how closely they adhere to the manual structure and whether or not they cover specific session content. Adherence items will clearly delineate the objectives for each session discussed in the second training component above. Proficiency scores will be based on group leaders' skillfulness in building rapport with the patient-participant and establishing a therapeutic environment conducive to the development of collaborative goals and action plans (e.g., used language that the patients could follow and understand, answered patient's questions and concerns). The measure also assesses skillfulness in the use of procedural techniques that are consistent with the objectives of the intervention (e.g., identified examples and assignments that matched the patient's needs. Group sessions will be audio-recorded when patient-participants agree to allow for fidelity ratings. Research staff will listen live via telephone to those group sessions where consent for audio-recording was not attained by all group participants. Group leaders who fall below an acceptable level will receive consultation by the study team to address areas of concern. No further patients will be assigned to these providers until these individual providers improve. We will provide verbal feedback to staff participants based on performance. Perceptions of client satisfaction with treatment. Patient-participants will rate their perceptions of

client satisfaction with their group leader following the last group session using an exit interview survey, The self-reported paper survey will ask all of the CSQ-8 items (rated on a 4-point Likert scale designed to measure client satisfaction with the services received), as well as additional questions about the EPIC experience. The exit interview survey also asks about interest in future follow up about satisfaction with the EPIC experience to identify a potential sample for future study (see Attachment 7). In addition to overall perceptions of client satisfaction, the exit interview provides a perception of the perceived value of service received; agreement between patient and provider about treatment goals and tasks; and the effective quality of their bond. The CSQ-8 measure has adequate internal consistency and overall scores (Cronbach's  $\alpha = .92-.93$ ) for 8-item scale.

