2) Objective ratings of fidelity along two dimensions: intervention adherence and intervention proficiency. Members of our study team have previously developed and tested a fidelity measure to objectively rate how well an individual has followed a behavioral or self-management support protocol during a one-on-one encounter with a patient. For the current study, the fidelity measure assesses adherence of the participant to the prescribed personalized goal-setting intervention protocol and the participant's proficiency, or rather, their skillfulness (e.g., building rapport and creating a therapeutic environment) in conducting the group sessions and/or the personalized goal-setting. These ratings are for the purpose of ensuring internal validity to the research. They will not be shared with participants' supervisors or negatively affect their job in any way. 3) We will also ask patient-participants to provide a self-report of their relationship with the PACT-member conducting their collaborative goal-setting sessions. We will use an Exit Interview survey (modified Client Satisfaction Questionnaire CSQ-8) (see Attachment 7) to determine patient-participants' perceptions of satisfaction with the service received from the study provider at the last EPIC session. Fidelity ratings of adherence and proficiency have been used in our previous trials along with the CSQ. Greater description of our fidelity ratings and CSQ measurements are provided below (**§5.1.G.a.**).

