**5.1.H.ii. Data Collection at Follow Up Assessments.** Post-intervention follow up assessments will be targeted for collection at 5-months after the date of randomization, with assessments occurring no earlier than 4 months after randomization and no later than 6 months after randomization. The assessment following the maintenance phase (Figure 3) will be targeted for collection at 10-months after the date of randomization. Self-reported measures at follow up assessments will be collected by central research staff via telephone using a structured data collection tool. To guide completion of the telephone interview, participants will be mailed blank assessment packets for reference. Blinded research staff will be trained to administer questionnaires by telephone at follow-up assessments and to instruct participants on how to accurately respond to questionnaires. A structured guide will steer participants through response options. We have implemented these procedures in previous studies to improve data collection and reduce missing data. Patient assessments will not be audio-recorded during the study.

Study staff, working with PACT clerical staff, will schedule a lab visit for HbA1c within 2 weeks of the target data collection time. When a clinical HbA1c lab value is available within the data collection window, it will be used for the research analysis.

Study staff will also perform chart abstraction of patient-level characteristics and clinical or PACT/facility variables that may account for confounding. The patient-level characteristics will include: weight, body mass index, Deyo comorbidity score, receipt of other related treatments (e.g. diabetes education), and primary care visits in the last 12 months.

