**5.1.H.iii. Attrition/Retention Estimates.** Given the benefits of the computerized patient record and our prior experience with VA participants, we expect that rates of missing data for primary outcomes will be <15%. While we may experience a lower adherence with EPIC group sessions, it is reasonable to anticipate having primary outcomes data for  $\geq 85\%$  of participants, as reflected in our sample size and power estimates. To handle missing data, we will conduct sensitivity analyses using tests for data missing completely at random and tests for nonrandom missingness. These analyses will allow us to evaluate whether the reasons for loss to follow-up at the various time periods are related to the observed values of the outcome variables. Additionally, we will plot the data over time to visually assess changes in outcomes from baseline to 1-year and to indicate whether additional terms are needed in the models to account for nonlinearity over time.

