HbA1c levels	X	X	X	X	Diet/Exercise	X	X	X
Diabetes Distress Scale		X	X	X	Pharmacy refills (database)	X	X	X
Baseline Covariates					Goal-Setting Evaluation Tool	X	X	X
Patient Activation Measure		X	X	X	Attendance in group visits		X	X
Functional Health Literacy measure		X			Post-intervention Implementation variables			
The Spoken Knowledge in Low Literacy in Diabetes (SKILLD) Knowledge Assessment Scale		X			Patient exit interviews (Attachment 7)		X	
Patient Socio-demographics		X			Clinician exit interviews (Attachment 13)			X
Baseline clinical characteristics		X			Summative implementation variables			
PACT and facility characteristics		X			Reach and Adoption measures	X	X	X
Patient knowledge & understanding of DM					Fidelity measures	X	X	X
EQ-5D		X	X	X				
		X	X	X				

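### The satisfaction exit survey is tied to the last EPIC session with no route for patients who stopped attending earlier, so the satisfaction result is at risk of selection bias

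*Combined protocol and SAP*

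**What the plan says.** Section 5.1.F.iii lists three fidelity strategies. The third is a patient exit survey, a modified CSQ-8, measuring "perceptions of satisfaction with the service received from the study provider at the last EPIC session". Section 5.1.G.a repeats the rule with slightly different scope: patients rate "client satisfaction with their group leader following the last group session using an exit interview survey". It also fixes the mode: "The self-reported paper survey will ask all of the CSQ-8 items", with added questions about the EPIC experience.

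Table 10 marks the patient exit interview once, apparently in the 4-month column (the table is broken in the text available).

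For the other follow-up measures, section 5.1.H.ii states: "Self-reported measures at follow up assessments will be collected by central research staff via telephone using a structured data collection tool". The interviewers are blinded, and patients follow along on paper, since "participants will be mailed blank assessment packets for reference".

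On attendance, section 5.1.H.iii says: "While we may experience a lower adherence with EPIC group sessions". It still expects primary outcome data for at least 85% of participants. Its figure of under 15% missing covers primary outcomes only.

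Section 5.6.C.iii names the CSQ as one of five candidate mediators of the EPIC versus EUC effect on post-intervention outcomes. The multiple imputation in section 5.6.C is specified for the outcome analyses; the exit survey is not mentioned there.

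**The concern.** A survey handed out at the final session reaches those who are still coming. EPIC patients who left the groups earlier, or who missed session 6, remain in the trial and are contacted for HbA1c and DDS, but no described step asks them for this rating. Respondents are thus selected by attendance, and attendance may well be related to satisfaction.

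Two uses are exposed. As a fidelity measure, mean satisfaction would describe those who stayed rather than those who were treated. In the mediation models, early leavers would have no CSQ value, so those models would in effect condition on attendance, which is itself determined after randomization. Section 5.1.G.a also uses the survey to find patients willing to be contacted for future study, and that pool would be selected in the same way.

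This point concerns selection within the EPIC arm. Whether and how the CSQ can be obtained in the EUC arm is a separate question.

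**Working it through.** **Figures in the plan.** The documents give no attendance rate, no exit-survey response rate and no satisfaction result, so there is no stated figure to reproduce. The size of the EPIC arm, used only for scale, does reproduce from section 5.6.A: 1 + (12 − 1) × 0.0183 = 1.2013; 100 × 1.2013 = 120; 120 / 0.85 = 141.2, rounded up to 142.

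**Is there another collection route in the text?**

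- Sections 5.1.F.iii and 5.1.G.a: paper form, at or after the last session. No mail, telephone or early-exit route.
- Table 10: a mark at one time point. This gives timing, not a method of collection.
- Section 5.1.H.ii: a telephone interview by blinded staff. A form asking about the EPIC experience would reveal the arm to the interviewer, so this call is not a ready substitute.
- Section 5.6.C: imputation for outcome analyses, silent on the survey.

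No described procedure, then, either collects the survey from early leavers or handles its missingness.

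**Size of the possible bias.** Let q be the share of EPIC patients without a survey, R the mean among respondents, N the mean that non-respondents would have given, and d = R − N. The mean over all is M = (1 − q)R + qN, so

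R − M = q × (R − N) = q × d.

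Section 5.1.G.a describes eight items on a 4-point scale. Scoring each item 1 to 4 (an assumption) gives a total from 8 to 32. Both q and d are assumed. Respondent counts apply q to all 142 for illustration.

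| q | d (points on total) | Overstatement q × d | Respondents of 142 |
|---|---|---|---|
| 0.20 | 2 | 0.4 | 114 |
| 0.35 | 3 | 1.05 | 92 |
| 0.50 | 4 | 2.0 | 71 |

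A wider grid shows how far the answer depends on the inputs. For q = 0.05, 0.15, 0.30 and 0.45, the shift in the total is:

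- absentees 1.0 point per item lower (d = 8): 0.4, 1.2, 2.4, 3.6;
- absentees 0.5 point per item lower (d = 4): 0.2, 0.6, 1.2, 1.8;
- absentees the same (d = 0): 0 throughout;
- absentees 0.25 point per item higher (d = −2): −0.1, −0.3, −0.6, −0.9.

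Nothing in the documents selects one row over another.

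**The case against.** Three arguments on the other side carry weight.

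First, a reader might infer that patients who leave the groups never rate the program. The documents do not go that far. Table 10 ties the exit interview to a follow-up time point, section 5.1.G.a says after rather than at the last session, and Attachment 7 is also cited for the DDS, medication adherence and goal-quality measures, so it may belong to a wider assessment packet. The attachment is not in the documents. What stands is that no route for early leavers is described and that the one existing follow-up contact is a poor fit because of blinding.

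Second, a reader might infer that the satisfaction result is certainly biased upward. Patients may stop because of transport, scheduling or illness, and the eligibility criteria show that the planners regarded transport and availability as real barriers. Section 5.1.H.iii is also conditional: adherence may be lower. Upward bias is the likelier direction but is not established.

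Third, it might seem that a program shedding its dissatisfied patients would look as good as one that satisfies everyone. The planned attendance reporting prevents this. Section 5.1.F.iii tracks sessions received against sessions prescribed, Table 5 reports the proportions attended for each enrolled patient, and the exploratory implementation analyses in section 5.6.C regress outcomes on attendance. Drop-out would be visible. Those measures do not, however, show how satisfied the leavers were, nor do they supply the missing mediator value.

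It is also true that satisfaction carries no hypothesis or threshold and does not enter the H2 or H3 models.

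**Conclusion.** The point holds as a risk of selection, not as a demonstrated bias. Followed as written, the rule yields satisfaction and CSQ mediator values mainly from EPIC patients still attending at the end, with no plan for the rest. The likely direction is upward. The illustrative size is 0.4 to 2.0 points on the 8–32 total if 20–50% are absent and would score 2–4 points lower, and zero if they would score the same. These inputs are assumptions, and the documents settle neither size nor sign. The HbA1c and DDS comparisons are unaffected. The change is still worth making, because the survey is one of three named fidelity strategies, the CSQ enters the mediation analysis, and the repair is cheap.

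**What to change.** - State in sections 5.1.F.iii and 5.1.G.a how and when the exit survey is collected, and bring them into line with Table 10.
- Offer it to every EPIC patient who attended at least one session, whatever their later attendance. A patient who attended none has no group leader or session provider to rate; report the number of such patients instead.
- For patients absent from the last session, use a separate mailing or a call from un-blinded staff in the 4–6 month window. Keep the form out of the packet used with blinded interviewers. The call option matters because section 5.1.H.i recognizes that patients with limited health literacy may not manage a written measure.
- Report the response rate and satisfaction by number of sessions attended.

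The cost is protocol wording and a few extra contacts by un-blinded staff, who already schedule the EPIC sessions. The drawbacks are some remaining non-response, including non-response related to literacy, and a slightly different timing or mode from patients who complete the form at the last session.
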